- k. Bone Marrow Aspiration: Bone marrow aspiration for cytogenetic analysis both by FISH and standard karyotyping, and morphologic evaluation including assessment of plasma cell percentage is required at screening/baseline (within 21 days prior to study drug administration. Bone marrow aspirate should be repeated if CR or stringent complete response (sCR) is suspected to confirm achievement of response according to IMWG criteria, and at End of therapy. Additional BM aspirate material (10-15cc if feasible) and biopsy for correlative studies are to be collected at baseline and any time a specimen is obtained to confirm response.
- Peripheral blood for correlative studies should be obtained at baseline, for phase 1 Day 1 of Cycles 1, 3, and 5 and for phase 2 on Day 1 of Cycles 2, 4, and 6 and at EOT for all patients. Four 10 mL tubes in total (3 green top, 1 red top/serum separator tube). Whole blood will be evaluated for circulating MM/plasma cells (and other mononuclear cells of interest); serum and plasma will be for evaluated for potentially relevant circulating cytokines, and surrogate markers of osteolytic activity.
- m. Myeloma-specific laboratory tests: β2 Microglobulin (at baseline only), serum and 24-hour urine immunoelectrophoresis, serum immunoglobulin assay, serum/urine immunofixation and serum FLC with kappa/lambda ratio to be performed at baseline, every cycle prior to study drug administration thereafter and at end of treatment (if last tests were > 4 weeks) and for patients who discontinue therapy for reasons other than disease progression. Myeloma laboratory tests will be repeated every month until disease progression or initiation of subsequent therapy. Response assessment will be done at the beginning of every cycle. Following pre-treatment evaluations on Day 1 of the first cycle evaluations may be performed on Day 1 of a subsequent cycle or during the 7 days prior to Day 1 of the Cycle as needed for scheduling. (Note that an evaluation performed during the final week of Cycle 1 should nonetheless be recorded as the evaluation for the beginning of Cycle 2, with similar assignments for subsequent cycles).

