11.6 Analyses of Efficacy Data

The study will preliminary evaluate the activity of the SL-410/POM/DEX regimen. Secondary efficacy endpoints will include: PFS and PFS-6; ORR (CR + VGPR + PR) and clinical benefit rate (CR + VGPR + PR + MR) based on IMWG defined response criteria, as well as DOR; and OS. Response rates and depth of response will be calculated as the percent of evaluable patients that have confirmed sCR/CR/VGPR or PR, and exact 95% confidence intervals will be calculated for these estimates. Time to response, duration of response, and survival will be estimated using the product-limit method of Kaplan and Meier. For subgroups of patients defined by disease and line of therapy, exact 1-sided 95% confidence intervals will be calculated

for ORR and clinical benefit rates, and the distributions for duration of response, PFS, PFS6, and OS will be estimated by Kaplan-Meier methodology.

Efficacy assessment parameters will include:

- M-protein determination using both of the following procedures:
 - SPEP and serum protein immunofixation with quantitative immunoglobulins; and
 - UPEP and urine protein immunofixation (all using the same 24-hour urine collection)
- Serum FLC
- BM to quantify percent MM cell involvement
- Plasmacytoma evaluation: PET/CT scan or MRI and or physical exam as clinically indicated
- Skeletal survey
- Serum β2 microglobulin
- Cytogenetic analysis/FISH from BM aspirate

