15.2 International Myeloma Working Group Response Criteria

Response	IMWG criteria
sCR	CR as defined below plus: normal FLC ratio and absence of clonal cells in bone marrow-by immunohistochemistry or 2 – 4 color flow cytometry
CR	 Negative immunofixation on the serum and urine and disappearance of any soft tissue plasmacytomas and < 5% plasma cells in bone marrow. In patients with only FLC disease, a normal FLC ratio of 0.26–1.65 is required.
VGPR	 Serum and urine M-protein detectable by immunofixation but not on electrophoresis or 90% reduction in serum M-protein plus urine M-protein level < 100 mg/24 h. In patients with only FLC disease, >90% decrease in the difference between involved and uninvolved FLC levels is required.
PR	 50% reduction of serum M-protein and reduction in 24 hours urinary M-protein by ≥90% or to < 200 mg/24 h If the serum and urine M-protein are unmeasurable, a ≥ 50% decrease in the difference between involved and uninvolved FLC levels is required in place of the M-protein criteria If serum and urine M-protein are not measurable, and serum free light assay is also not measureable, ≥ 50% reduction in plasma cells is required in place of M-protein, provided baseline bone marrow plasma cell percentage was ≥ 30% In addition to the above listed criteria, if present at baseline, a ≥ 50% reduction in the size of soft tissue plasmacytomas is also required
Minimal response in patients with RRMM adapted from the EMBT criteria	 ≥ 25% but < 49% reduction of serum M protein and reduction in 24 hour urine M protein by 50 – 89%, which still exceeds 200 mg/24hrs. In addition to above; if present at baseline, 25-49% reduction in the size of soft tissue plasmacytomas is also required No increase in size or number of lytic bone lesions (development of compression fractures does not exclude response)
Stable Disease	Not meeting criteria for CR, VGPR, PR or progressive disease

Response	IMWG criteria
Progressive	Increase of ≥ 25% from lowest response value in any 1 of the following:
disease	 Serum M-component (the absolute increase must be ≥ 0.5 g/dL)⁴ and/or
	 Urine M-component (the absolute increase must be ≥ 200 mg/24 h) and/or
	 Only in patients without measurable serum and urine M-protein, the difference between involved and uninvolved FLC levels. The absolute increase must be > 10 mg/dL

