	 Only in patients without measurable serum and urine M-protein and without measurable disease by FLC levels, bone marrow plasma cell percentage (absolute % must be ≥ 10%)
	 Definite development of new bone lesions or soft tissue plasmacytomas or definite increase in the size of existing bone lesions or soft tissue plasmacytomas
	 Development of hypercalcemia (corrected serum calcium > 11.5 mg/dL) that can be attributed solely to the plasma cell proliferative disorder

All relapse categories (CR, sCR, VGPR, and progressive disease) require 2 consecutive assessments made at any time before the institution of any new therapy; complete response and PR and SD categories also require no known evidence of progressive or new bone lesions if radiographic studies were performed. VGPR and CR categories require serum and urine studies regardless of whether disease at baseline was measurable in serum, urine both or either. Radiographic studies are not required to satisfy these response requirements. Bone marrow assessments need not be confirmed. For progressive disease, serum M-component increases of ≥ 1 gm/dl are sufficient to define response if starting M-component is ≥ 5 g/dl.

IMWG clarification for coding progressive disease: Clarified that Bone marrow criteria for progressive disease are to be used only in patients without measurable disease by M protein and by FLC levels. Clarified that 25% increase refers to M protein, FLC, and bone marrow results and does not refer to bone lesions, soft tissue plasmacytomas or hypercalcemia. Note the lowest response value does not need to be a confirmed value.

FreeLite™ Disease Response Criteria

Complete Response: For those patients being followed by serum free light chain (and NO measurable serum or urine M-spike), which were immunofixation negative at enrollment, normalization of serum free light chain ratio.

Normalization is defined as the serum free light chain ratio being within the normal range. If the serum free light chain ratio is not within the normal range, but the individual kappa and lambda light chain values are within normal range, this may be considered CR.

Partial Response: If only measurable parameter is serum immunoglobulins FLC, EITHER of the following changes quality as partial response:

- A 50% decrease in the difference between involved and uninvolved FLC levels; OR
- A 50% decrease in the level of involved FLC AND a 50% decrease (or normalization) in the ratio of involved/uninvolved FLC

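### Appendix 15.2 gives two conflicting complete-response rules for patients with only free light chain disease: one demands a normal ratio, the other may accept an abnormal one

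*Protocol*

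**What the plan says.** Appendix 15.2 holds two sets of response rules under one International Myeloma Working Group title: a response table and, below it, a FreeLite block.

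- **Table, CR row.** Besides negative immunofixation, it asks for "disappearance of any soft tissue plasmacytomas and < 5% plasma cells in bone marrow". For FLC-only disease it adds: "In patients with only FLC disease, a normal FLC ratio of 0.26–1.65 is required".
- **Table, VGPR row.** "In patients with only FLC disease, >90% decrease in the difference between involved and uninvolved FLC levels is required". The PR row asks for a fall of at least 50% in that difference when M-protein cannot be measured.
- **FreeLite block, CR.** It applies to a defined group: "For those patients being followed by serum free light chain (and NO measurable serum or urine M-spike), which were immunofixation negative at enrollment". CR is normalization of the ratio. A further sentence covers an abnormal ratio: "but the individual kappa and lambda light chain values are within normal range, this may be considered CR". Marrow and plasmacytomas are not mentioned.

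Inclusion criterion 6 (Section 5.2) admits patients on FLC alone, with an involved chain of at least 100 mg/L and an abnormal ratio. Section 11.2.3 classifies evaluable patients by these criteria, and Section 11.6 reports the result: "Response rates and depth of response will be calculated as the percent of evaluable patients" with confirmed sCR, CR, VGPR or PR. Table 13, note k, adds: "Bone marrow aspirate should be repeated if CR or stringent complete response (sCR) is suspected to confirm achievement of response".

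**The concern.** One rule makes a normal ratio a condition of CR. The other lets the assessor waive that condition when each chain is individually normal. The patients whom FreeLite describes have FLC-only disease, so both rules apply to them. No sentence says which governs, and the word *may* leaves the choice to whoever makes the call.

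The trial is open-label (Section 11.8) and the protocol describes no central review of response. Two sites with identical laboratory values could therefore enter different best responses, and the depth-of-response table would mix two definitions of CR.

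**Working it through.** The plan states no figure that depends on this rule, so there is none to reproduce. The check applies both rules to the same patient.

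**Inputs from the protocol**
- Ratio is kappa/lambda (Table 13, note m); normal is 0.26–1.65 (Appendix 15.2).
- Difference = involved minus uninvolved FLC. VGPR needs a fall above 90%, PR at least 50% (Appendix 15.2).
- Entry floor: involved FLC 100 mg/L (Section 5.2).
- 20 patients at the phase 2 dose (Section 11.3).

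**Assumed, because the protocol gives no limits for single chains**
- Normal ranges: kappa 3.3–19.4 and lambda 5.7–26.3 mg/L.
- Baseline uninvolved chain: 5 mg/L.

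**Kappa disease at the entry floor**
- Baseline: kappa 100, lambda 5; difference 95.
- On treatment: kappa 18, lambda 7, both within the assumed ranges.
- Ratio = 18/7 = 2.57, above 1.65, so abnormal.
- Difference = 11; fall = (95 − 11)/95 = 88.4%.
- Table: not CR (ratio), not VGPR (88.4% is below 90%), hence PR. FreeLite: may be CR.

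**Same final values, higher baseline**
- Baseline: kappa 300, lambda 5; difference 295.
- Fall = (295 − 11)/295 = 96.3%. Table: VGPR. FreeLite: may be CR.

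**Lambda disease**
- Final lambda 18, kappa 7: ratio 7/18 = 0.39, which is normal. The two ratio rules agree.
- Final lambda 20, kappa 4: ratio 4/20 = 0.20, abnormal with both chains in range. From baseline lambda 100, kappa 5, the difference goes from 95 to 16, a fall of 83.2%. Table: PR. FreeLite: may be CR.

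**Where the table gives PR rather than VGPR**

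The fall is 90% or less when the baseline difference is at most 10 times the residual difference. At the largest residual that keeps both chains normal:

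| Assumed ranges (mg/L) | Kappa disease | Lambda disease |
|---|---|---|
| kappa 3.3–19.4, lambda 5.7–26.3 | 10 × 13.7 = 137 | 10 × 23.0 = 230 |
| kappa 4–15, lambda 6–20 | 10 × 9 = 90 | 10 × 16 = 160 |
| kappa 3–25, lambda 5–30 | 10 × 20 = 200 | 10 × 27 = 270 |

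Above these baseline differences the table gives VGPR.

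**Is the patient still a responder under the table?** With the uninvolved chain at 5 mg/L at baseline, the smallest fall across the three range sets is 1 − 27/95 = 71.6%, so the table always gives at least PR. Going below 50% takes an extreme combination: the widest ranges, the largest residual, and a baseline kappa of 100 mg/L with the ratio only just above 1.65. The baseline difference is then 100 − 100/1.65 = 39.4 and the fall 1 − 20/39.4 = 49.2%. The ratio would have risen from 1.65 to 5.0 on treatment, so I set that case aside.

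**Effect on the CR rate.** One patient in 20 is 5 percentage points. The exact 95% interval is 0–16.8% for 0/20 and 0.1–24.9% for 1/20.

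**The case against.** The best defence is that the consequence is small. The affected analysis is secondary and descriptive, no decision rule uses the CR rate, and the one hypothesis with a stated power is PFS-6 (Section 11.3). A patient is affected only if FLC-only, immunofixation negative at enrollment, and left with an abnormal ratio while both chains normalize. All of that stands, and it sets the severity. It does not reconcile a mandatory ratio with a discretionary exception to it.

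Four stronger readings are tempting and are not supported.

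- **That FreeLite drops the marrow and plasmacytoma conditions.** It is silent on them and waives neither. Note k of Table 13 still asks for a repeat aspirate when CR is suspected, and Section 9.3.1 lists aspiration where needed to confirm response. FreeLite can fairly be read as replacing only the FLC element of CR. What remains is that the appendix does not say so.
- **That the disagreement is generally two categories, CR against PR.** That holds near the entry floor. At higher baselines the table gives VGPR, one category away.
- **That every FLC-only patient is exposed.** Assuming 10–20% of 20 patients have FLC-only disease gives 2–4 patients, but only those meeting the conditions above can be reclassified. The documents give no basis for that smaller count.
- **That response rate or progression-free survival is compromised.** This conflict is confined to CR. The two blocks also word PR and progression differently, but those are separate matters and nothing here depends on them.

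**Conclusion.** The contradiction is real and sits in current, intact text: Appendix 15.2 both requires a normal ratio for CR in FLC-only disease and permits CR without one, with no order of precedence. The same patient can be CR under FreeLite but VGPR, or PR near the entry floor, under the table.

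The size is 5 points of CR rate per reclassified patient at n = 20; the number of such patients is unknown and probably very small. The category assignments rest on assumed single-chain normal ranges and an assumed baseline uninvolved chain of 5 mg/L. The textual conflict rests on neither. Overall response rate, clinical benefit rate, PFS-6 and the MTD are not affected by this point. It is an internal inconsistency of minor severity.

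**What to change.** In Appendix 15.2, do one of the following:

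- state that the response table prevails over the FreeLite block for CR; or
- delete the sentence that allows CR with an abnormal ratio.

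In either case, add that the FreeLite CR rule replaces only the FLC element of the CR row, so that the marrow condition (plasma cells below 5%) and the plasmacytoma condition still apply.

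The cost is one or two sentences in the appendix, with no change to sample size, visits or procedures. The reported CR rate may be slightly lower than under the permissive rule.

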15.3 Definition of Lines of Therapy

A line of therapy is defined as 1 or more cycles of a planned treatment program. This may consist of 1 or more planned cycles of single-agent therapy or combination therapy, as well as a sequence of treatments administered in a planned manner. For example, a planned treatment approach of induction therapy followed by autologous stem cell transplantation, followed by maintenance is considered 1 line of therapy. A new line of therapy starts when a planned course of therapy is modified to include other treatment agents (alone or in combination) as a result of disease progression, relapse, or toxicity. A new line of therapy also starts when a planned period of observation off therapy is interrupted by a need for additional treatment for the disease.

15.4 Definition of Relapsed and Refractory Myeloma

Refractory Myeloma:

Refractory myeloma is defined as disease that is non-responsive (failure to achieve minimal response or develops progressive disease while on therapy) while on primary or salvage therapy, or progresses within 60 days of last therapy. There are 2 categories of refractory myeloma.

- Relapsed and refractory myeloma: Relapsed and refractory myeloma is defined as
 disease that is non-responsive while on salvage therapy or progresses within 60 days of
 last therapy in patients who have achieved minimal response or better at some point
 previously to then progressing in their disease course.
- Primary refractory myeloma: refractory myeloma is defined as disease that is nonresponsive in patients who have never achieved minimal response or better with any
 therapy. It includes patients who never achieve MR or better in whom there is no
 significant change in M protein and no evidence of clinical progression; as well as
 primary refractory, progressive disease where patients meet criteria for true progressive
 disease.

Relapsed myeloma

Relapsed myeloma is defined as previously treated myeloma which progresses and requires the initiation of salvage therapy but does not meet the criteria for either primary refractory myeloma or relapsed and refractory myeloma.

15.5 CYP Enzymes Inhibitors

Strong Inhibitors (≥ 5-fold increase in AUC or > 80% decrease in CL)

Ciprofloxacin, enoxacin, fluvoxamine

Moderate inhibitors (≥ 2 but < 5-fold increase in AUC or 50-80% decrease in CL)

Methoxsalen, mexiletine, oral contraceptives, phenylpropanolamine, thiabendazole, zileuton

Weak inhibitors (≥ 1.25 but < 2-fold increase in AUC or 20-50% decrease in CL)

Acyclovir, allopurinol, caffeine, cimetidine, daidzein, disulfiram, echinacea, famotidine, norfloxacin, propafenone, propranolol, terbinafine, ticlopidine, verapamil

Classification of In Vivo Inhibitors of CYP Enzymes:

http://www.fda.gov/Drugs/DevelopmentApprovalProcess/DevelopmentResources/DrugInteractionsLabeling/ucm093664.htm#classInhibit

15.6 The New York Heart Association Classification of Cardiac Disease

The following table presents the NYHA classification of cardiac disease:

Class	Functional Capacity	Objective Assessment
I	Patients with cardiac disease but without resulting limitations of physical activity. Ordinary physical activity does not cause undue fatigue, palpitation, dyspnea, or anginal pain.	No objective evidence of cardiovascular disease.
II	Patients with cardiac disease resulting in slight limitation of physical activity. They are comfortable at rest. Ordinary physical activity results in fatigue, palpitation, dyspnea, or anginal pain.	Objective evidence of minimal cardiovascular disease.
Ш	Patients with cardiac disease resulting in marked limitation of physical activity. They are comfortable at rest. Less than ordinary activity causes fatigue, palpitation, dyspnea, or anginal pain.	Objective evidence of moderately severe cardiovascular disease.
IV	Patients with cardiac disease resulting in inability to carry on any physical activity without discomfort. Symptoms of heart failure or the anginal syndrome may be present even at rest. If any physical activity is undertaken, discomfort is increased.	Objective evidence of severe cardiovascular disease.

15.7 Estimated Creatinine Clearance rate (eCCr) using Cockcroft-Gault Formula

$$eC_{Cr} = \frac{(140 - \mathrm{Age}) \times \mathrm{Mass} \; (\mathrm{in \; kilograms}) \times [0.85 \; if \; Female]}{72 \times \mathrm{Serum \; Creatinine} \; (\mathrm{in \; mg/dL})}$$
